1.1 Primary Objective

1.1.1. To determine the maximum tolerated dose of BYL719 with capecitabine and radiation for patients with newly diagnosed rectal cancer.

1.2 Secondary Objectives

- 1.2.1 To evaluate the safety of BYL719 with capecitabine and radiation for patients with rectal cancer.
- 1.2.2. To evaluate the pathologic complete response for patients with rectal cancer treated with BYL719, capecitabine and radiation.
- 1.2.3. To assess the surgical complication rate of patients receiving preoperative BYL179 capecitabine and radiation
- 1.2.4. To gather preliminary information as to whether mutations in KRAS, BRAF, or PIK3CA predict pathologic complete response to BYL719, capecitabine and radiation.

2.0 BACKGROUND

Rectal Cancer: There are approximately 41,000 new cases of rectal cancer diagnosed each year in the United States.¹ Stage-for-stage, recurrence rates are higher in rectal cancer in comparison to colon cancer.²

Preoperative Chemoradiation: Chemoradiation improves survival in patients with rectal cancer.³⁻⁵ Preoperative fluoropyrimidine (fluorouracil or capecitabine) with concurrent radiation is a standard of care for stage II/III rectal cancer.⁶ Preoperative chemoradiation improves local control and is associated with reduced toxicities as compared to postoperative chemoradiation.⁶ Pathologic complete response rates for fluorouracil and radiation range are approximately 9-25%.⁶⁻¹⁰ When added to fluoropyrimidine, no other agent (including oxaliplatin, irinotecan, EGFR inhibitors, or bevacizumab) increases pathologic complete response.¹¹⁻¹⁴

There are three classes of PI3Ks grouped according to structure and function. Class IA PI3K is the one most clearly implicated in human cancer. Class IA PI3Ks consist of a regulatory subunit and a catalytic subunit. Three mammalian genes, PIK3R1, PIK3R2, and PIK3R3, encode p85 α , p85 β and p55 γ regulatory subunits, respectively, which by convention are referred to collectively as p85. The catalytic isoforms, p110 α , p110 β , and p110 γ , are the products of three genes, PIK3CA, PIK3CB, and PIK3CD. Both PIK3CA and PIK3R1 can be somatically mutated in colorectal cancer, and these mutations promote activation of the PI3K pathway.

BYL719: BYL719 is an oral small-molecule inhibitor of the p110α catalytic subunit of PI3K, which is encoded by the *PIK3CA* gene, one of the most commonly mutated genes in human cancers including rectal cancer. BYL719 inhibits proliferation of PI3Kα-driven cancer cell lines in vitro and causes regression of *PIK3CA*-mutant tumor models in vivo. A phase I study has been completed in patients with advanced solid tumors carrying a somatic mutation of *PIK3CA*.³³ Thirty-six patients received doses up to 450 mg/day. The maximum tolerated dose (MTD) for once-daily dosing was declared as 400 mg/day. Dose limiting toxicities (DLTs) were hyperglycemia, nausea, vomiting, and diarrhea. The most common BYL719-related adverse events were hyperglycemia (49%), nausea (45%), diarrhea (40%), decreased appetite (38%), vomiting (30%), and fatigue (27%). Partial responses were seen in 7 patients and seventeen patients stayed on study for >24 weeks demonstrated proof-of-concept of the importance of this pathway.

PI3K Inhibitors are Radiation Sensitizers: Resistance of tumors to radiation has been associated with the activation of intracellular signaling pathways, particularly the PI3K/AKT pathway. Preclinical studies have shown the enhanced effect of radiation in combination with PI3K/AKT/mTOR in several cancer cell lines including colon cancer. He et al reported that the local recurrence rate following preoperative chemoradiation for rectal cancer is three times higher in patients with PI3K mutations thanin patients without PI3K mutations.²⁴

Strategy to Develop BYL719 With Capecitabine and Radiation in Rectal Cancer: PIK3 signaling is increased in many rectal cancers. ²⁴⁻²⁹ Upregulation of PIK3 predicts radiation resistance. ²¹ PI3K inhibitors are radiation enhances. Thus the addition of BYL719 to capecitabine and radiation may improve pathologic complete response rates for rectal cancer. In this phase I study, any patient with rectal cancer needing preoperative radiation will be eligible since upregulation of PIK3 may occur in the absence of a mutation. This phase I study will provide the necessary preliminary data to study BYL719 within the developing framework of NRG where patients with rectal cancer will be treated with a targeted agent that correlates with the specific mutation detected in an individual tumor. It is anticipated that BYL719 will be dramatically effective as a radiation sensitizer in the 12% of patients with rectal cancer and PI3K mutations so phase II/III investigations of BYL719 within the cooperative group may focus on rectal cancers with PI3K mutations.

The Brown University Oncology Research Group is a national leader in the management of rectal cancer: Total Neoadjuvant Treatment (TNT): The Brown University Oncology Research Group has successfully piloted the concept of total neoadjuvant treatment for rectal cancer in a 39 patient study. 34,35 Patients with stage II and stage III rectal cancer received 8 cycles of FOLFOX, followed by capecitabine and concurrent radiation followed by surgery. Compliance to neoadjuvant FOLFOX was far superior to the traditional treatment paradigm when FOLFOX is administered after rectal surgery. NRG (the merger of the NSABP and the RTOG) has chosen the TNT approach to be the new standard treatment sequence for stage II-III rectal cancer. This approach is optimal for developing a targeted radiation sensitizer. During neoadjuvant FOLFOX, molecular testing can be performed. Based on the molecular profile of an individual tumor a specific radiation enhancer such as a PI3K inhibitor may be added when preoperative radiation is initiated based on the mutational status of the tumor.

Future Development of BYL719 in Rectal Cancer Following Demonstration of Safety in This Proposed Phase I Study: The current research focus of NRG is to develop a more promising regimen of radiation enhancement than capecitabine alone. Once safety of BYL719 with capecitabine/radiation is established, BYL719 can be definitively tested in NRG. It is envisioned that within the cooperative groups, new patients with rectal cancer will be treated within the TNT format with 8 cycles of FOLFOX followed by capecitabine and radiation. New patients with rectal cancer will be evaluated for specific molecular alterations. If a P13K mutation were detected, within this multi-institutional cooperative group framework, the effect of BYL719 on pathologic complete response could be definitively tested within the subgroup of patients with PI3K mutations. An agent that increases pathologic complete response would be a major advance in rectal cancer because it would decrease the number of patients with low rectal cancer requiring a permanent colostomy. The primary goal of this Brown University Oncology Research Group is to determine that a safe dose of BYL719 can be administered with capecitabine and radiation in patients with rectal cancer. Therefore, the threshold of success for this phase I study is to establish safety. In a subsequent NRG study, within the TNT framework, a randomized phase II study will be planned exclusively in patients with PIK3CA mutations to assess whether pathologic complete response is improved within this specific subgroup of patients.

3.0 PATIENT ELIGIBILITY

3.1 Conditions for Patient Eligibility

- 3.1.1 Patients must have histologically proven adenocarcinoma of the rectum with no evidence of distant metastases.
- 3.1.2 The tumor must be clinically Stage II (T3-4 N0) or stage III (N+). Stage of the tumor may be determined by CT scan, endorectal ultrasound or MRI. (For patients receiving chemotherapy prior to protocol chemoradiation, the initial clinical stage applies. CT/MRI/PET should be performed within 2 months of study entry to exclude disease progression.) For the MTD expansion phase only: patients who are stage IV, and in whom it is planned to administer capecitabine and radiation then have a resection of their rectal cancer, are also eligible. Submit documentation to BrUOG on location of metastatic disease sites with source confirmation (scan, pathology etc) and obtain confirmation that patients would meet this criterion.
- 3.1.3 Measurable disease not required at baseline. Patient's without measurable disease may be enrolled as long as they clinically meet stage II or III criteria or for MTD expansion phase: also stage IV.
- 3.1.4 Patients must not have received pelvic radiation for rectal cancer, or prior pelvic radiation for any other malignancy that would prevent the patient from receiving the required radiation treatments for this study. (Patients may receive neoadjuvant chemotherapy prior to study chemoradiation)
- 3.1.5 Patients must not have an active concurrent invasive malignancy. Patients with prior malignancies, , are eligible if they are deemed by their physician to be at low risk for recurrence. For example, patients with squamous or basal cell carcinoma of the skin, melanoma in situ, carcinoma of the cervix, early stage breast cancer, or carcinoma in situ of the colon that have been effectively treated are eligible, even if these conditions were diagnosed within 3 years prior to registration.
- 3.1.6 Patients must be \geq 18 years of age,
- 3.1.7 ECOG performance status 0-1

3.1.8 ANC \geq 1,000/µl, platelets \geq 100,000/µl, total bilirubin \leq ULN (except for patients with Gilbert's syndrome who may only be included if total bilirubin is \leq 3xULN with direct bilirubin within normal range),

ALT \leq 2.5xULN, AST \leq 2.5xULN,

fasting plasma glucose \leq 140 mg/dL and HbA1c \leq 6.4% (both criteria have to be met),

 $HGB \ge 9.0g/dL$.

Serum creatinine < 1.5xULN and/or creatinine clearance > 50% LLN

Potassium, Calcium and Magnesium (corrected for albumin) within normal range or \leq grade 1 if determined not clinically significant by treating investigator (must send to BrUOG in writing)

INR ≤ 1.5

- * For patients with FPG \geq 100 mg/dL and/or HbA1c \geq 5.7% (i.e. threshold for pre-diabetes) at screening, recommend lifestyle changes according to ADA guidelines, i.e. dietary advice (e.g. small frequent meals, low carbohydrate content, high fiber, balancing carbohydrate intake over the course of the day, three small meals and 2 small snacks rather than one large meal) and exercise. A consultation with a diabetologist is highly recommended
- 3.1.9 Patient is able to swallow and retain oral medication. Patients with feeding tubes are considered not able to retain oral medication, as this drug can not be suspended through a feeding tube.
- 3.1.10 LVEF within institutional normal limits (must submit what these are) or >50%
- 3.1.11 Signed informed consent and is able to comply with study and/or follow-up procedures.
- 3.1.12 QTcF <480 msec
- 3.1.13 Patients history of diarrhea has been review and patient has been informed of potential study drug induced diarrhea and management. This must be documented by treating MD. See section 5 for baseline assessments of patient history of diarrhea.

3.2 Exclusion Criteria

- 3.2.1 Patient has a known hypersensitivity to any of the excipients of BYL719 (alpelisib)
- 3.2.2 For stage II and III patients: Suspected or confirmed metastatic disease including CNS involvement. For stage IV patients: CNS involvement.
- 3.2.3 Patient with clinically manifest diabetes mellitus, or documented steroid induced diabetes mellitus
- 3.2.4 Patient with impaired gastrointestinal (GI) function or GI disease that may significantly alter the absorption of oral BYL719 (e.g. ulcerative disease, uncontrolled nausea, vomiting, diarrhea, malabsorption syndrome, or small bowel resection). Patients with colostomies are allowed unless colostomy is for one of the precluded reason above.
- 3.2.5 Patient who has not recovered to grade 1 or better (except alopecia) from related side effects of any prior antineoplastic therapy
- 3.2.6 Patient who has had systemic therapy within 4 weeks of starting study drug BYL719 (6 weeks for nitrosoureas or mitomycin C).
- 3.2.7 Patient who has undergone major surgery \leq 4 weeks prior to starting study treatment or in the investigators opinion who has not recovered from side effects of such procedure
- 3.2.8 Patient has any of the following cardiac abnormalities:

2/15/15, 2/19/15, 3/20/15, 3/27/15,4/23/15, 6/11/15, 6/11/15, 7/13/15, 8/14/15, 8/17/15, 8/26/15, 8/31/15, 9/3/15, 9/8/15 approved Novartis, 9/11/15, 9/14/15, 9/21/15, RNEXECPI 9/29/15, 10/5/15 novartis, 10/6/15 approved Novartis, 10/8/15, 10/19/12 sent FDA, 11/4/15 clinical hold, 11/5/15 sent Novartis, SMP 11/6/15, 11/20/20/15, Amendment # 1 5/6/16, Amendment # 2 6/2/16, Amendment # 3 10/31/16 –FDA Reviewer edits, Amendment #3 updated 1/19/2017, Amendment # 4 6/20/17, Amendment # 5 8/9/2017 with IB 10, AMENDMENT #6 1/16/18

- A. symptomatic Congestive heart failure
 - i. history of documented congestive heart failure (New York Heart Association functional classification III-IV), documented cardiomyopathy
 - ii. Left Ventricular Ejection Fraction (LVEF) <50% as determined by Multiple Gated acquisition (MUGA) scan or echocardiogram (ECHO)
- B. myocardial infarction ≤ 6 months prior to enrollment
- C. unstable angina pectoris
- D. serious uncontrolled cardiac arrhythmia
- E. symptomatic pericarditis
- F. QTcF > 480 msec on the screening ECG (using the QTcF formula)
- 3.2.9 Patient who is currently receiving medication with a known risk of prolonging the QT interval or inducing Torsades de Pointes (TdP) and the treatment cannot either be discontinued or switched to a different medication prior to starting study drug treatment. To be documented and submitted to BrUOG with registration. Please refer to appendices F and G.
- 3.2.10 Patient who has participated in a prior investigational cancer treatment study within 30 days prior to enrollment. This refers to treatment not follow-up.
- 3.2.11 Patient is currently receiving warfarin or other coumarin derived anti-coagulant, for treatment, prophylaxis or otherwise. Therapy with heparin, low molecular weight heparin (LMWH), or fondaparinux is allowed. To be documented and submitted to BrUOG with registration. Eliquis is allowed.
- 3.2.12 Patient is currently receiving treatment with drugs known to be strong inhibitors or inducers of isoenzyme CYP3A. The patient must have discontinued strong inducers for at least one week and must have discontinued strong inhibitors before the start of treatment. Switching to a different medication prior to registration is allowed; (Refer to Section Concomitant Medication, Appendix F and G). To be documented and submitted to BrUOG with registration via conmed list. Patient must not be on any medications in Appendix G
- 3.2.13 Patient with known positive serology for human immunodeficiency virus (HIV)
- 3.2.14 Patient with any other condition that would, in the Investigator's judgment, preclude patient's participation in the clinical study due to safety concerns or compliance with clinical study procedures, e.g. infection/inflammation, intestinal obstruction, unable to swallow oral medication, social/psychological complications, chronic active hepatitis, severe hepatic impairment etc
- 3.2.15 Patients who have other concurrent severe and/or uncontrolled medical conditions that would, in the Treating Physician's judgment, contraindicate patient participation in the individual patient program (eg. active or uncontrolled severe infection, chronic active hepatitis, immuno-compromised, acute or chronic pancreatitis, uncontrolled high blood pressure, interstitial lung disease, etc.)
- 3.2.16 Patient has a history of non-compliance to medical regimen or inability to grant consent
- 3.2.17 Pregnant or nursing (lactating) women, where pregnancy is defined as the state of a female after conception and until the termination of gestation, confirmed by a positive hCG laboratory test (> 5 mIU/mL). Pregnancy test not required for patients who are considered post-menopausal and not of childbearing potential as defined below.

Women are considered post-menopausal and not of child-bearing potential if they have had 12 months of natural (spontaneous) amenorrhea with an appropriate clinical profile (e.g. age appropriate,

history of vasomotor symptoms) or have had surgical bilateral oophorectomy (with or without hysterectomy) at least six weeks ago.

For women with therapy-induced amenorrhea, oophorectomy or serial measurements of FSH and/or estradiol are needed to ensure postmenopausal status.

- 3.2.18 Patient who does not apply highly effective contraception during the study and through the duration as defined below after the final dose of study treatment:
- a. Sexually active males (unless surgically sterilized at least 6 months prior to screening which would mean no contraception is needed) should use a condom during intercourse while taking drug and for 6 months after the final dose of study treatment and should not father a child in this period, but may be recommended to seek advice on conservation of sperm. The use of spermicidal foam is also highly suggested to be used with a condom as another form of protection. A condom is required to be used also by vasectomized men in order to prevent delivery of the drug via seminal fluid. Males should be cautioned to not donate sperm while actively receiving treatment on study.
- b. Women of child-bearing potential, defined as all women physiologically capable of becoming pregnant, must use highly effective contraception during the study and through 6 months after the final dose of study treatment. Highly effective contraception is defined as either:
 - i. Total abstinence: When this is in line with the preferred and usual lifestyle of the subject. [Periodic abstinence (e.g., calendar, ovulation, symptothermal, postovulation methods) and withdrawal are not acceptable methods of contraception].
 - ii. Female sterilization: have had surgical bilateral oophorectomy (with or without hysterectomy) or tubal ligation at least six weeks before taking study treatment. In case of oophorectomy alone, only when the reproductive status of the woman has been confirmed by follow up hormone level assessment
 - iii. Male partner sterilization (with the appropriate post-vasectomy documentation of the absence of sperm in the ejaculate). [For female study subjects, the vasectomized male partner should be the sole partner for that patient]
 - iv.Use a combination of the following (both a+b):
 - a. Placement of an intrauterine device (IUD) or intrauterine system (IUS)
 - b. Barrier methods of contraception: Condom or Occlusive cap (diaphragm or cervical/vault caps) with spermicidal foam/gel/film/cream/vaginal suppository.

Note: Hormonal contraception methods (e.g. oral, injected, and implanted) are not allowed as BYL719 may decrease the effectiveness of hormonal contraceptives.

- c. Women are considered post-menopausal and not of child-bearing potential if they have had 12 months of natural (spontaneous) amenorrhea with an appropriate clinical profile (e.g. age appropriate, history of vasomotor symptoms) or have had surgical bilateral oophorectomy (with or without hysterectomy) at least six weeks ago.
- b. For women with therapy-induced amenorrhea, oophorectomy or serial measurements of FSH and/or estradiol are needed to ensure postmenopausal status.

NOTE: Ovarian radiation or treatment with a luteinizing hormone-releasing hormone (LH-RH) agonist (goserelin acetate or leuprolide acetate) is not permitted for induction of ovarian suppression.

* Please consult with local product labels should any combination agents or concomitant medications be used, as this period may be longer for other potentially genotoxic compounds.

A female is considered post-menopausal and not of child-bearing potential if they have had 12 months of natural (spontaneous) amenorrhea with an appropriate clinical profile (e.g. age appropriate, history of vasomotor symptoms) or have had surgical bilateral oophorectomy (with or without hysterectomy) at least six weeks ago before the treatment start.

For females with therapy-induced amenorrhea, oophorectomy or serial measurements of Follicle-Stimulating Hormone (FSH) and/or estradiol are needed to ensure postmenopausal status.

NOTE: Ovarian radiation or treatment with a luteinizing hormone-releasing hormone (LH-RH) agonist (goserelin acetate or leuprolide acetate) is not permitted for induction of ovarian suppression.

- 3.2.19 Herbal preparations/medications are not allowed throughout the study. These herbal medications include, but are not limited to: St. John's wort, Kava, ephedra (ma huang), gingko biloba, dehydroepiandrosterone (DHEA), yohimbe, saw palmetto, Medical Marijuana and ginseng. Patients need to stop using these herbal medications 7 days prior to first dose of study drug. 3.2.20 Patient must not eat or drink Seville orange (and juice), grapefruit or grapefruit juice, grapefruit hybrids, pummelos, starfruits and cranberry juice from 7 days prior to the first dose of study drug and during the entire study treatment
- 3.2.21 Patient is currently receiving or has received systemic corticosteroids ≤ 2 weeks prior to day 1 of study drug, or who has not fully recovered from side effects of treatment. The following uses of corticosteroids are permitted: single doses, topical applications (e.g., for rash), inhaled sprays (e.g., for obstructive airways diseases), eye drops or local injections (e.g., intra-articular).
- 3.2.22 Patient is concurrently using other anti-cancer therapy

3.3 Re-Screening:

If a patient signs consent and then screen fails (does not meet the eligibility criteria) and the treating MD requests that the patient be re-screened outside of the 28 day screening window, sites are to contact BrUOG who will assess patients on a case by case basis. Depending on many diverse factors including the conditions that are being evaluated, the reasons why patient initially screen failed, and the nature of the initial results, re-screening may or may not be medically/scientifically appropriate. BrUOG should be made aware of such a situation with at least 72 hours and provided with information on screen-failure.

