4.2.1 Permitted concomitant therapy

Antiemetics

Use of anti-emetics is allowed. Prophylactic anti-emetics should be started only once the patient experiences nausea or vomiting, at the discretion of the investigator. It is recommended that patients use drugs that do not cause QT prolongation (Appendix F). Please note that some anti-emetics have a known risk for TdP and are prohibited (refer to Appendix G)

Oral hypoglycemic anti-diabetic Agents

Patients who develop diabetes mellitus during the study should be treated according to the ADA (American Diabetes Association) guidance. It is recommended to start treatment with glimepiride, glibenclamide or metformin. Patients receiving oral antidiabetics which are predominantly metabolized by CYP2C9 and CYP2C8, including but not limited to, repaglinide, rosiglitazone, glipizide and tolbutamide, must be carefully monitored for hypoglycemia as BYL719 was found to be moderate reversible inhibitor of these enzymes (refer to Appendix F).

Anticoagulation

Anticoagulants other than warfarin/coumarin derivates may be administered under the discretion of the investigator. However, caution is advised when BYL719 is co-administered with antiplatelet pro-drugs such as clopidogrel, ticlopidine and prasugrel, which require metabolic activation by CYP3A4, CYP2C9 and CYP2C19. BYL719 has the potential to inhibit these enzymes and may therefore decrease the metabolic activation and clinical efficacy of these pro-

drugs. Patients using anti-platetet pro-drugs should be carefully monitored (refer to Appendix F).

Contraceptives

Hormonal contraceptives may be affected by cytochrome P450 interactions, and are therefore not considered effective for this study. For allowed contraception methods, refer to Exclusion Criteria. Highly effective contraception should be maintained throughout the study and for 6 months after study treatment discontinuation.

CYP450 substrates

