Non-measurable disease: All other lesions (or sites of disease), including small lesions (longest diameter <10 mm or pathological lymph nodes with ≥ 10 to <15 mm short axis).

^C- The operative note and pathology note will be sent to BrUOG. Documentation of post op complications to be submitted to BrUOG as well.

^D post-menopausal women (surgical menopause or lack of menses \ge 12 months) do not need to have a pregnancy test, document status. If HCG is not drawn, sites are asked to document menopausal status on lab form.

^E It is appropriate to use labs from screening for day 1, if labs are within 14 days. It is appropriate to use physical, weight, vitals, toxicity assessment, concomitant medication, performance status from screening for day 1 if within 14 days. Labs and assessments for all subsequent cycles are to occur within (-)3 days prior to day 1 of treatment of each week. This means that if RT and BYL719 begin on a Monday, the week of treatment is M-Sunday and therefore labs are to be done within (-) 3 days prior to dosing/treatment Monday. An additional day is provided for a holiday so that if there is a Monday holiday, assessments can be done on Friday to cover both BYL719 treatment Monday and Radiation Tuesday.

F Adverse event evaluation will be done 2 and 4 weeks (30 days post last dose) and SAEs will be captured for 30 days post last dose of study drug, capecitabine or last radiation treatment, whichever ends last. If AE evaluation cannot be done exactly 30 days post last treatment (radiation, capecitabine or study drug, whatever is the last date of treatment), a one week window is provided (+1 week). SAEs occurring outside this 30 day window must be reported if the event is considered to be possibly related to the drug. If a patient begins a new treatment, AE evaluation will be stopped unless the patient experiences an event (AE or SAE) that is thought to be possibly related to the study treatment. BrUOG must be made aware of new treatment with start date.

^G Physical exam to be done in coordination with 30 day AE assessment only (+ 1 week window), No physical exams are required post 30 day post last dose of drug assessment.

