(y/n) Patient who is currently receiving medication with a known risk of prolonging the QT interval or inducing Torsades de Pointes (TdP) and the treatment cannot either be discontinued or switched to a different medication prior to starting study drug treatment. To be documented and submitted to BrUOG with registration.
(y/n) Patient who has participated in a prior investigational cancer treatment study within 30 days prior to enrollment. This refers to treatment not follow-up.
(y/n) Patient with known positive serology for human immunodeficiency virus (HIV)
(y/n) Patients who have other concurrent severe and/or uncontrolled medical conditions tha would, in the Treating Physician's judgment, contraindicate patient participation in the individual patient program (eg. active or uncontrolled severe infection, chronic active hepatitis, immuno-compromised, acute or chronic pancreatitis, uncontrolled high blood pressure, interstitial lung disease, etc.) (y/n) Patient with any other condition that would, in the Investigator's judgment, preclude patient's participation in the clinical study due to safety concerns or compliance with clinical study procedures, e.g. infection/inflammation, intestinal obstruction, unable to swallow oral medication, social/psychological complications, chronic active hepatitis, severe hepatic impairment etc
(y/n) Patient has a history of non-compliance to medical regimen or inability to grant consent
(y/n) Patient is currently receiving treatment with drugs known to be strong inhibitors or inducers of isoenzyme CYP3A or that prolong QT interval (see eligibility for more details.
(y/n) Patient is currently receiving warfarin or other coumarin derived anti-coagulant, for treatment, prophylaxis or otherwise. Therapy with heparin, low molecular weight heparin (LMWH), or fondaparinux is allowed
(y/n) Pregnant or breastfeeding. Women of child bearing potential must have a negative serum or urine pregnancy test (<5mIU/mL) within 14 days prior to beginning of treatment. Postmenopausal women do not need to have a pregnancy test, please document status. See eligibility for more details. See exclusion for definition of post-menopausal.
(y/n) Patient who does not apply highly effective contraception during the study and through the duration as defined below after the final dose of study treatment as defined in eligibility

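### Section 3.2.18 a both waives and requires condoms for men vasectomized at least 6 months before screening (minor internal inconsistency)

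*Combined protocol and SAP*

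**What the plan says.** Section 3.2.18 excludes patients who do not apply highly effective contraception, and part a sets out the rules for men. Its opening sentence asks sexually active men to use a condom during intercourse while on drug and for 6 months after the final dose. A parenthesis attached to the subject of that sentence removes some of them: "unless surgically sterilized at least 6 months prior to screening which would mean no contraception is needed". Further on in the same paragraph comes: "A condom is required to be used also by vasectomized men in order to prevent delivery of the drug via seminal fluid".

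Three other places in the document bear on contraception.

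- Section 4.2.1, under Contraceptives, refers the reader back: "For allowed contraception methods, refer to Exclusion Criteria". It then adds that highly effective contraception is to continue through the study and for 6 months after treatment stops.
- The inclusion part of the eligibility checklist (Appendix B) asks for willingness to use effective contraception on treatment and for at least 6 months afterwards.
- The exclusion part of the same checklist repeats the stem of 3.2.18 and leaves the detail to the protocol, with the period running "after the final dose of study treatment as defined in eligibility".

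**The concern.** The two sentences of 3.2.18 a give opposite instructions to the same man. The criterion is operative: section 8.0 requires sites to confirm each inclusion and exclusion element at registration, so staff have to apply this text. A site that stops at the parenthesis can tell a vasectomized man that he needs no condom and can cite the protocol for it.

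What is at stake is the partner's exposure to drug in semen, which the same paragraph sets out to prevent. The protocol also attends to partners elsewhere: section 11.3.1 requires pregnancy outcomes to be collected for female partners of treated men.

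**Working it through.** No arithmetic applies. The check is to apply the two sentences of 3.2.18 a to each kind of sexually active man, and then to see whether any other section decides the conflicting case.

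| Sexually active man | Opening sentence with its parenthesis | Later sentence on vasectomized men | Result |
|---|---|---|---|
| Not sterilized | Condom on drug and for 6 months after | Does not apply | Consistent |
| Vasectomized less than 6 months before screening | Condom on drug and for 6 months after (parenthesis not met) | Condom required | Consistent |
| Vasectomized at least 6 months before screening | Exempt | Condom required | Conflict |

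Two readings might remove the conflict in the last row.

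1. *The parenthesis concerns birth control only, and the later sentence concerns drug exposure.* This is a fair guess at what was meant. Grammatically, however, the exemption qualifies the men who are told to use a condom, so it takes away the condom instruction itself.
2. *The later sentence concerns recent vasectomies only.* It sets no limit on time since surgery, and its reason does not depend on that time.

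Next, the other sections.

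- Section 4.2.1 has one sentence that leads back to 3.2.18 and one that asks for 6 months of highly effective contraception after discontinuation. The second has no sterilization exemption, so it weighs against the parenthesis. It does not mention condoms for vasectomized men.
- The checklist inclusion line likewise has no sterilization exemption and gives a period of at least 6 months. It too says nothing about condoms for vasectomized men.
- The checklist exclusion line leads back to the eligibility section and adds no rule.

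The rest of the document therefore leans towards the later sentence without stating the rule for these men. The consent form is not among the material available, so nothing is concluded from it.

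On size: section 17.0 plans approximately 24 patients. The documents give neither the sex split nor the frequency of vasectomy, so the number affected cannot be computed. It can only be described as a subset of those 24.

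**The case against.** The strongest answer is that the paragraph resolves itself. The later sentence is the more specific one, its word *also* extends the condom duty just described, and its reason holds whether or not a man is fertile. Someone who reads to the end of the paragraph is told what to do. This largely stands: the intent is clear, and that is why the point is minor. It does not make the parenthesis harmless, because the parenthesis is still in force and says the opposite.

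A reader might infer more than the documents support, in four ways.

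- *That the protocol gives no period for vasectomized men.* The later sentence states none, but *also* naturally carries over the period in the opening sentence, and section 4.2.1 and the checklist inclusion line both give 6 months for contraception generally.
- *That sites would enrol such men differently.* The stem of 3.2.18 excludes for lack of contraception, whereas this condom serves to keep drug from the partner. Whether a sterile man without condoms is ineligible, or simply owes a precaution on study, is not stated. Different enrolment is possible but not shown.
- *That the waiver was a deliberate design decision.* Nothing suggests this. The two sentences look like a drafting inconsistency.
- *That the pregnancy-test waiver in footnote D of section 6.0 is a comparable defect, since it describes menopause more briefly than 3.2.17.* The checklist requires a negative test for women of child-bearing potential and directs the reader: "See exclusion for definition of post-menopausal". Section 8.0 requires each criterion to be confirmed. Those safeguards cover it, and it forms no part of this point.

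**Conclusion.** The inconsistency is real and minor. For men vasectomized at least 6 months before screening, 3.2.18 a gives two incompatible instructions. The later one is evidently the intended rule, and no other available section states the condom rule for them outright. The practical consequence is narrow: a site relying on the parenthesis would leave out a barrier that the protocol requires for the partner's protection.

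The conclusion assumes that surgical sterilization in the parenthesis includes vasectomy, which is its ordinary meaning for a man. It assumes nothing about how many such men will enrol. Dose escalation, DLT assessment, the MTD and the sample size are unchanged.

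**What to change.** In 3.2.18 a, delete the parenthesis containing "unless surgically sterilized at least 6 months prior to screening which would mean no contraception is needed". The opening sentence then covers every sexually active man, vasectomized or not: condom while taking drug and for 6 months after the final dose. The later sentence can stay as it is, since it explains why vasectomized men are included and now takes its period from the opening sentence.

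The cost is one deletion in the next amendment. No visit, test, dosing rule, cohort rule or sample size changes. If the consent form repeats the exemption, it should be aligned at the same time.
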